10.7.6 RETENTION OF RECORDS

The US FDA regulations (21 CFR §312.62[c]) and the ICH Guideline for GCP require that records and documents pertaining to the conduct of this study and the distribution of investigational drug, including eCRFs, ICFs, laboratory test results, and medication inventory records, must be retained by the Investigator for 2 years after the last marketing application approval in an ICH region or after at least 2 years have elapsed since formal discontinuation of clinical development of the study drug. All state and local laws for retention of records also apply. No records should be disposed of without the written approval of the Sponsor. Written notification should be provided to the Sponsor prior to transferring any records to another party or moving them to another location. For studies conducted outside the US under a US Investigational New Drug (IND), the Investigator must comply with the record retention requirements set forth in the US FDA IND regulations and the relevant national and local health authorities, whichever is longer.

[figure not shown]
All primary data, or copies thereof (e.g., laboratory records, eCRFs, data sheets, correspondence, photographs, and computer records), which are a result of the original observations and activities of the study and are necessary for the reconstruction and evaluation of any study report will be retained in the study site archives.

APPENDIX A – CLINICAL LABORATORY EVALUATIONS

Chemistry Panel (Fasted at least 8 hours):

Alanine aminotransferase
Albumin
Alkaline phosphatase
Aspartate aminotransferase
Blood urea nitrogen
Calcium
Chloride
Cholesterol
Creatinine
Creatine kinase/Creatine phosphokinase
Glucose
Potassium
Sodium
Total bilirubin
Total protein
Triglycerides
Uric acid

Complete Blood Count:

Hematocrit
Hemoglobin
Mean corpuscular hemoglobin
Mean corpuscular hemoglobin concentration
Mean corpuscular volume
Platelet count
Red blood cell (RBC) count
RBC distribution width
White blood cell (WBC) count
WBC differential (absolute):
 Basophils
 Eosinophils
 Lymphocytes
 Monocytes
 Neutrophils

Urinalysis:

Bilirubin
Color and appearance
Glucose
Ketones
Leukocyte esterase
Nitrite
Occult blood
pH and specific gravity
Protein
Urobilinogen
Microscopic exam including bacteria, casts, crystals, epithelial cells, RBCs, and WBCs (if protein, leukocyte esterase, nitrite, or blood is positive)

Drug Screen:

Including but not limited to the following:

Alcohol (ethanol)^a
Amphetamines
Barbiturates
Benzodiazepines
Cannabinoids (THC)
Cocaine (metabolite)
Methadone
Opiates
Phencyclidine
Cotinine^b

^a Alcohol breath testing will be performed at Check-in (Day -1) only.

^b Measured at the Screening visit only.

Other Tests:

Hepatitis B virus core antibody^b
Hepatitis B surface antigen^b
Hepatitis C virus antibody^b
Human immunodeficiency virus antibody^b
Pregnancy test (females of childbearing potential only; serum qualitative)
Follicle-stimulating hormone (postmenopausal females only)^b

APPENDIX B – APPROXIMATE MAXIMUM BLOOD VOLUME COLLECTED

Note: Additional samples may be drawn for safety purposes.

	Sample Volume (mL)	Number of Samples	Total Volume (mL)
Serology	7.0	1	7.0
Chemistry Panel (includes serum pregnancy and FSH)	8.5	5	42.5
CBC (hematology)	4.0	5	20.0
PK Samples	4.0	30	120
		Total	189.5

CBC = complete blood count; FSH = follicle-stimulating hormone; PK = pharmacokinetic.

3 ABBREVIATIONS

Abbreviations pertain to the SAP only (not the TFLs).

ADaM	Analysis Data Model
AE	adverse event
AUC	area under the concentration-time curve
AUC _{0-∞}	area under the concentration-time curve extrapolated to infinity
AUC _{0-t}	area under the concentration-time curve from Hour 0 to the last measurable concentration
BLQ	below the limit of quantification
CDISC	Clinical Data Interchange Standards Consortium
CI	confidence interval
CL/F	apparent systemic clearance
C _{max}	maximum observed concentration
CSR	Clinical Study Report
C _t	last measurable concentration
CV	coefficient of variation
CV _W	within-subject coefficient of variation
ECG	electrocardiogram
ICH	International Conference on Harmonisation
λ _z	apparent terminal elimination rate constant
MR _{AUC}	metabolite ratio based on AUC _{0-∞}
NC	not calculated
NR	no result
PK	pharmacokinetic
QTcB	QTc calculated using the Bazett correction
QTcF	QTc calculated using the Fridericia correction
R	Reference formulation
R ²	adjusted coefficient for determination of exponential fit
SAP	Statistical Analysis Plan
T	Test formulation
TEAE	treatment-emergent adverse event
TFLs	tables, figures, and listings

t_{\max}	time to maximum observed concentration
t_{last}	time of last measurable concentration
$t_{1/2}$	apparent terminal elimination half-life
V_z/F	apparent volume of distribution during the terminal elimination phase

4 INTRODUCTION

This SAP has been developed after review of the clinical study protocol (Final Version 1 dated 05 November 2018).

This SAP describes the planned analysis of the safety, tolerability, and PK data from this study. A detailed description of the planned TFLs to be presented in the Clinical Study Report (CSR) is provided in the accompanying TFL shell document.

The intent of this document is to provide guidance for the statistical analyses of PK data. In general, the analyses are based on information from the protocol, unless they have been modified by agreement between Genentech, Inc. and Covance Clinical Development Services. A limited amount of information concerning this study (e.g., objectives, study design) is given to help the reader's interpretation. This SAP must be finalized prior to the lock of the clinical database for this study. When the SAP and TFL shells are agreed upon and finalized, they will serve as the template for this study's CSR.

This SAP supersedes the statistical considerations identified in the protocol; where considerations are substantially different, they will be so identified. If additional analyses are required to supplement the planned analyses described in this SAP, they may be performed and will be identified in the CSR. Any substantial deviations from this SAP will be agreed upon between Genentech, Inc. and Covance EC Biometrics and identified in the CSR.

This SAP is written with consideration of the recommendations outlined in the International Conference on Harmonisation (ICH) E9 guideline entitled, "Guidance for Industry: Statistical Principles for Clinical Trials" and the ICH E3 guideline entitled, "Guidance for Industry: Structure and Content of CSRs."^{1,2}

5 STUDY OBJECTIVES

5.1 Primary objective

The primary objective of this study is:

- To demonstrate bioequivalence between entrectinib polymorph Forms A and C under fasted conditions in healthy adult male and female subjects.

5.2 Secondary objective

The secondary objective of this study is:

- To explore the safety and tolerability of a single 200-mg oral dose of entrectinib polymorph Forms A and C in healthy adult male and female subjects.

6 STUDY ENDPOINTS

6.1 Primary Endpoints

The primary endpoints are:

- The geometric mean ratios and associated 90% confidence intervals (CIs) of entrectinib and M5 metabolite PK parameters area under the concentration-time curve from Hour 0 to the last measurable concentration (AUC_{0-t}) and maximum observed concentration (C_{max}).

6.2 Secondary Endpoints

The secondary endpoints are:

- Incidence and severity of adverse events (AEs) and incidence of abnormalities in laboratory safety tests, 12-lead electrocardiograms (ECG) and vital sign measurements.

7 STUDY DESIGN

[figure not shown]
This is a randomized, open-label, 2-treatment, 2-period, 2-way crossover study to demonstrate bioequivalence between entrectinib polymorph Forms A and C administered under fasted conditions in healthy male and female subjects. In each treatment period, subjects will receive a single 200-mg oral dose of entrectinib while fasted. It is planned that a total of 28 subjects will receive the following 2 treatments in a randomized sequence:

Treatment A: Single 200-mg oral dose of entrectinib F06 capsule formulation Form A (Reference formulation [R])

Treatment C: Single 200-mg oral dose of entrectinib F06 capsule formulation Form C (Test formulation [T])

An overview of the study design is provided in Figure 1.

Figure 1 Overview of Study Design

* Minimum 14 days between study drug administrations in Periods 1 and 2.

† Relative to study drug administration in Period 1.

‡ Relative to study drug administration in Period 2.

Potential subjects will be screened to assess their eligibility to enter the study within 27 days (Days -28 to -2) prior to study entry. Replacement subjects may be enrolled, only if deemed necessary by the Sponsor, to ensure that 26 subjects complete the study (have evaluable PK data for both Periods 1 and 2).

Eligible subjects will be admitted to the study site on the day prior to entrectinib dosing (Check-in [Day -1] of Period 1) to collect baseline data and to familiarize the subjects with study procedures that will be used during the rest of the study. On Day 1 of Period 1, subjects will be randomly assigned to 1 of 2 treatment sequences (i.e., TR or RT) according to a pre-specified randomization scheme based on the order of study enrollment. The assigned treatments will be administered under fasted conditions on Day 1 of each period. Doses of entrectinib will be separated by a washout period of at least 14 days.

8 TREATMENTS

The following is a list of the study treatment abbreviations and ordering that will be used in the TFLs.

Study Treatment Name	Abbreviation	Treatment Order on TFLs
Single 200-mg oral dose of entrectinib F06 capsule formulation Form C (Test)	Form C	1
Single 200-mg oral dose of entrectinib F06 capsule formulation Form A (Reference)	Form A	2

The following is a list of the study treatment sequence abbreviations and ordering that will be used in the baseline TFLs.

Study Treatment Sequence	Abbreviation	Treatment Sequence Order on TFLs
Single 200-mg oral dose of entrectinib F06 capsule formulation Form C (Test) /Single 200-mg oral dose of entrectinib F06 capsule formulation Form A (Reference)	Form C / Form A	1
Single 200-mg oral dose of entrectinib F06 capsule formulation Form A (Reference) /Single 200-mg oral dose of entrectinib F06 capsule formulation Form C (Test)	Form A / Form C	2

9 SAMPLE SIZE JUSTIFICATION

A total of 28 subjects will be enrolled to ensure that 26 subjects complete the study and have evaluable PK data from both treatment periods.

In a previous study (Study RXDX-101-15), the within-subject coefficients of variation (CV) for entrectinib area under the concentration-time curve extrapolated to infinity ($AUC_{0-\infty}$) and C_{max} following administration of a single dose of entrectinib were estimated to be 20% and 16%, respectively. Assuming a true ratio of 1.05 between the geometric means of Test and Reference treatments, and a within-subject CV of 21%, 26 evaluable subjects are needed to ensure there is

at least 90% probability that the 90% CI for the treatment ratios fall within the no-effect boundaries of 0.80 and 1.25 for each of the 2 primary PK parameters ($AUC_{0-\infty}$ and C_{max}).

10 DEFINITION OF ANALYSIS POPULATIONS

The **Safety Population** will consist of all subjects who received at least 1 dose of study drug and have at least 1 postdose safety assessment.

The **PK Population** will consist of all subjects who received at least 1 dose of study drug and have at least 1 evaluable postdose PK sample. A subject may be excluded from the PK summary statistics and statistical analysis if the subject has an AE of vomiting that occurs at or before 2 times median time to maximum observed concentration.

All protocol deviations that occur during the study will be considered prior to database lock for their severity/impact and will be taken into consideration when subjects are assigned to analysis populations. Details of subject assignment to the analysis populations will be listed.

The **All Subjects Population** will be consistent with the Safety Population.

11 STATISTICAL METHODOLOGY

11.1 General

Data listings will be provided for the All Subjects Population. Summary statistics and statistical analyses will be performed for subjects included in the relevant analysis populations (Safety/PK).

For continuous data, summary statistics will include the arithmetic mean, arithmetic standard deviation, median, minimum, maximum, and number. For log-normal data (e.g. the PK parameters: area under the concentration-time curves [$AUCs$] and C_{max}) the geometric mean and geometric CV will also be presented. For categorical data, frequency count and percentages will be presented. Data listings will be provided for all subjects up to the point of withdrawal, with any subjects excluded from the relevant population highlighted. For the calculation of summary statistics and statistical analysis, unrounded data will be used.

Missing values will not be imputed, with the possible exception of missing PK predose concentrations, as detailed in [Section 11.4.2](#).

Data analysis will be performed using SAS[®] Version 9.4.

Analysis Data Model (ADaM) datasets will be prepared using Clinical Data Interchange Standards Consortium (CDISC) ADaM Version 2.1, and CDISC ADaM Implementation Guide Version 1.1. Pinnacle 21 Community Validator Version 2.2.0 will be utilized to ensure compliance with CDISC standards.

11.1.1 Definition of Baseline and Change from Baseline

Period specific baseline for each parameter is defined as the last value measured prior to dosing in each period, including repeat (vital signs and ECGs) and unscheduled (clinical laboratory parameters) readings (see [Section 11.1.2](#) for definitions of repeat and unscheduled readings).

Mean change from period specific baseline is the mean of all individual subjects' change from baseline values. Each individual change from baseline will be calculated by subtracting the individual subject's baseline value from the value at the timepoint. The individual subject's change from baseline values will be used to calculate the mean change from baseline using a SAS procedure such as Proc Univariate.

11.1.2 Repeat and Unscheduled Readings

Repeat readings occur when the original vital signs or ECG result requires confirmation. Repeat readings are labelled as 'Repeat' in the listings and replace the original readings in all summaries and changes from baseline presentations and calculations. Prior to dosing, all readings taken in addition to the original reading are defined as predose repeats. Postdose repeat readings are defined as readings collected within 15 minutes of the actual time of the original reading.

With the exception of predose results described above, unscheduled readings for vital signs or ECGs are defined as readings collected >15 minutes from the actual time of the original reading. Unscheduled readings are labelled as 'Unscheduled' in the listings. Because unscheduled readings are not associated with any scheduled timepoint, they are excluded from all summaries (with the exception that they may be used as baseline, as stated in [Section 11.1.1](#)).

11.2 Demographics and Subject Disposition

The demographic variables age, sex, race, ethnicity, body weight, height, and body mass index will be summarized and listed. Subject disposition will be summarized and listed.

11.3 Prior and Concomitant Medications

Prior and concomitant medications will be coded using the World Health Organization (WHO) Drug Dictionary (Version September 2018 Enhanced Dictionary Version B3 format [or higher if version is updated during the study]). Prior and concomitant medications will be listed separately.

11.4 Pharmacokinetic Assessment

11.4.1 Pharmacokinetic Analysis

The following PK parameters will be determined where possible from the plasma concentrations of entrectinib and M5 using non-compartmental methods performed using Phoenix WinNonlin (Certara USA, Inc., Version 6.4 or higher):

Parameter	Definition
C_{\max}	maximum observed concentration
t_{\max}	time to maximum observed concentration
t_{last}	time of last measurable concentration
AUC_{0-t}	area under the concentration-time curve from Hour 0 to the last measurable concentration, calculated using the linear trapezoidal rule for increasing concentrations and the logarithmic rule for decreasing concentrations
$AUC_{0-\infty}$	area under the concentration-time curve extrapolated to infinity, calculated using the formula: $AUC_{0-\infty} = AUC_{0-t} + (C_t/\lambda_z)$ where C_t is the last measurable concentration and λ_z is the apparent terminal elimination rate constant
λ_z	apparent terminal elimination rate constant, where λ_z is the magnitude of the slope of the linear regression of the log concentration versus time profile during the terminal phase
$t_{1/2}$	apparent terminal elimination half-life (wherever possible), where $t_{1/2} = \text{natural log}(\ln 2)/\lambda_z$
CL/F	apparent systemic clearance, calculated as dose/ $AUC_{0-\infty}$ (entrectinib only)
V_z/F	apparent volume of distribution during the terminal elimination phase, calculated as $CL/F/\lambda_z$ (entrectinib only)
MR_{AUC}	metabolite ratio based on $AUC_{0-\infty}$ (M5 only)

Additional PK parameters may be determined where appropriate.

The PK analysis will, where possible, be carried out using actual postdose times recorded in the raw data. If actual times are missing, nominal times may be used with sponsor approval.

Concentrations will be used as supplied by the analytical laboratory for PK analysis. The units of concentration and resulting PK parameters, with amount or concentration in the unit, will be presented as they are received from the analytical laboratory.

The C_{\max} , t_{\max} , and t_{last} will be obtained directly from the plasma concentration-time profiles.

For multiple peaks, the highest postdose concentration will be reported as C_{\max} . In the case that multiple peaks are of equal magnitude, the earliest t_{\max} will be reported.

The metabolic ratios (MR_{AUC}) will be calculated as follows:

$$MR_{AUC} = \frac{AUC_{0-\infty} \text{ metabolite}}{AUC_{0-\infty} \text{ parent drug}}$$

The AUC_{0-t} or other common partial area may be used to determine metabolite ratios (MR_{AUC}) if $AUC_{0-\infty}$ cannot be reliably calculated for the majority of subjects.

11.4.1.1 Criteria for Handling Concentrations that are Missing or Below the Limit of Quantification in Pharmacokinetic Analysis

- Concentration values that are below the limit of quantification (BLQ) will be set to zero, with defined exceptions as follows;
 - Any embedded BLQ value (between 2 quantifiable concentrations) and BLQ values following the last quantifiable concentration in a profile will be set to missing for the purposes of PK analysis.
 - If there are late positive concentration values following 2 BLQ concentration values in the apparent terminal phase, these values will be evaluated. If these values are considered to be anomalous, they will be set to missing.
 - If an entire concentration-time profile is BLQ, the profile will be excluded from the PK analysis.
 - If a predose concentration is missing, these values may be set to zero.

11.4.1.2 Criteria for the Calculation of an Apparent Terminal Elimination Half-Life Number of Data Points

- At least 3 data points will be included in the regression analysis and preferably should not include C_{max} .

Goodness of Fit

- When assessing terminal elimination phases, the adjusted coefficient for determination of exponential fit (R^2 adjusted) will be used as a measure of the goodness of fit of the data points to the determined line.
- Regression-based parameters (i.e., λ_z , $t_{1/2}$, $AUC_{0-\infty}$, CL/F , V_z/F , MR_{AUC}) will only be calculated if the R^2 adjusted value of the regression line is ≥ 0.7 .

Period of Estimation

- The time period used for the estimation of $t_{1/2}$, where possible, will be over at least 2 half-lives.
- Where an elimination half-life is estimated over a time period of < 2 half-lives, it will be flagged in the data listings at the discretion of the Pharmacokineticist, and the robustness of the value should be discussed in the study report.

Calculation of AUC

- The minimum requirement for the calculation of AUC will be the inclusion of at least 3 consecutive plasma concentrations above the lower limit of quantification, with at least 1 of these concentrations following C_{max} .
- For any partial AUC determination (where applicable), nominal time will generally be used for the end of the interval. Actual times for partial AUC intervals may be used at the discretion of the Pharmacokineticist.
- The $AUC_{0-\infty}$ values (and related parameters [CL/F , V_z/F , MR_{AUC}]) where the percentage extrapolation is less than 30% will be reported. Any $AUC_{0-\infty}$ values (and related parameters) where the percentage extrapolation is $\geq 30\%$ will be reported and flagged but excluded from descriptive statistics.

Anomalous Values

- If a value is considered to be anomalous due to being inconsistent with the expected PK profile, it may be appropriate to exclude this point from the PK analysis. However, the exclusion of data must have strong justification and will be documented in the raw data and study report.
- Embedded BLQ values may be considered anomalous depending on the route of administration and the characteristics of the drug.
- If a PK profile has a quantifiable predose value that is $>5\%$ of its respective C_{max} value, all concentrations and PK parameters for the given PK profile may be excluded from the summary statistics of PK tables and statistical analysis at the discretion of the Pharmacokineticist.

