7.2.2 DOSE PREPARATION AND ADMINISTRATION

Each unit dose will be prepared by qualified clinical staff based on the study randomization that will be provided by a Covance Biostatistician.

The assigned treatment will be administered on Day 1 of each period:

Treatment A: Entrectinib F06 capsule formulation Form A (Reference formulation)

Treatment C: Entrectinib F06 capsule formulation Form C (Test formulation)

Each dose will be administered orally with approximately 240 mL of room temperature water after an overnight fast (minimum 8 hours). A hand and mouth check will be performed to verify that the dose administered was swallowed. Subjects will be instructed not to crush, split, or chew the entrectinib capsules. Subjects will continue to fast for at least 4 hours following entrectinib dosing.

Water (except water provided with entrectinib dosing) will be restricted 1 hour prior to and 1 hour after each entrectinib administration, but will be allowed ad libitum at all other times.

Doses of entrectinib will be separated by a washout period of at least 14 days.

Appropriate unit doses, as described above, will be administered to consecutively numbered subjects. Although the timing of events requires that each subject will be consistently administered the appropriate dose at specific times, the exact dose time of consecutive subjects may be staggered to obviate the need to have all subjects on precisely the same study schedule. For each dose, the subject's actual time will be recorded in the source documents and transcribed into the eCRFs.

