11.4.3 Presentation of Pharmacokinetic Parameters

- For the calculation of summary statistics of PK parameters, all NR and NC values in a data series will be set to missing.
- The AUC values will be set to NC if they have been calculated using fewer than 3 concentrations, and/or 3 concentrations if the last is C_{max} .

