11.4.4 Pharmacokinetic Statistical Methodology

Descriptive statistics (mean, median, minimum, maximum, standard deviation, geometric mean, and geometric CV will be calculated for all PK parameters and PK concentration data. Plasma concentrations of entrectinib and its active metabolite M5, and derived plasma PK parameters, will be listed and summarized by treatment using descriptive statistics. Individual and mean concentration versus time profiles will be plotted.

The primary parameters for bioequivalence testing will be C_{max} and AUC_{0-t} of entrectinib. Statistical analysis for M5 primary parameters, C_{max} and AUC_{0-t} will be provided as supportive evidence. For each analyte, if t_{last} notably varies between the treatments, then AUC calculated over a common partial area may be included in the statistical analysis. If $AUC_{0-\infty}$ is reliably calculated, this will be used for analysis. A linear mixed model⁵ will be applied to analyze the log-transformed (base e)⁴ primary PK parameters. The model will include fixed effects for treatment, period, and sequence, and a random effect for subject within sequence. Estimates of geometric mean ratios on the original scale, together with the corresponding 90% CIs, will be derived for the comparisons between Test and Reference treatments. Bioequivalence will be concluded if the 90% CIs for the treatment ratios fall within the no-effect boundaries of 0.80 and 1.25 for AUCs and C_{max} ³.

An example of the SAS code that will be used (assuming trtmnt coding is 1= Form A, 2= Form C) is as follows:

```
proc mixed data=xxx;
  class sequence subject period trtmnt;
  model l_pk = sequence period trtmnt / ddfm=kr;
  random intercept / subject=subject(sequence);
  estimate 'Test - Ref' trtmnt -1 1 / cl alpha=0.1;
  lsmeans trtmnt;
run;
```

where l_{pk} is the log-transformed (base e) PK parameter.

Within-subject coefficients of variation (CV_w) will be calculated for AUCs and C_{max} based on the log-normal distribution using the following formula:

$$CV_w(\%) = [\exp(mse) - 1]^{\frac{1}{2}} \times 100$$

where mse is the residual error from the mixed model.

Residual plots will be produced to assess the adequacy of the model.

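### Automatic exclusion of entirely BLQ profiles takes a capsule of either form that released no measurable drug out of the bioequivalence test

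*SAP*

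**What the plan says.** SAP 11.4.1.1 opens with a general rule, "Concentration values that are below the limit of quantification (BLQ) will be set to zero, with defined exceptions as follows", and lists among the exceptions: "If an entire concentration-time profile is BLQ, the profile will be excluded from the PK analysis". No condition on cause, review or documentation is attached. The SAP's other exclusion provisions are softer. The vomiting exclusion (SAP 10) is optional and tied to an adverse event. The exclusion for a high predose value (SAP 11.4.1.2) is left to the pharmacokineticist. Removing an anomalous value (same section) needs well-founded reasons recorded in the report.

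For sparse profiles, SAP 11.4.1.2 makes an AUC depend on "the inclusion of at least 3 consecutive plasma concentrations above the lower limit of quantification", at least one of them after Cmax. SAP 11.4.3 adds "The AUC values will be set to NC if they have been calculated using fewer than 3 concentrations" and, for summary statistics, "all NR and NC values in a data series will be set to missing". Cmax has no such minimum; SAP 11.4.1 reads it directly from the profile.

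Downstream, SAP 11.1 states "Missing values will not be imputed, with the possible exception of missing PK predose concentrations". SAP 11.4.4 analyses natural-log parameters: "The model will include fixed effects for treatment, period, and sequence, and a random effect for subject within sequence". The 90% CIs for Cmax and AUC must lie within 0.80 to 1.25. Neither document gives a sensitivity analysis or substitute value for a profile without quantifiable drug. On dosing, Protocol 7.2.2 says "A hand and mouth check will be performed to verify that the dose administered was swallowed".

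**The concern.** The study compares how two polymorphs perform in vivo (Protocol 2.2). A capsule that releases no measurable drug is the extreme case of the difference under test, and here the exclusion is triggered by that outcome. Swallowing is checked, and 14 postdose samples run to 96 hours for a drug with a half-life of about 20 to 30 hours. An all-BLQ profile would therefore point mainly to the product or to a sampling or assay error. The rule treats these alike and asks about neither.

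An excluded profile yields no Cmax and no AUC0-t, nothing may be imputed, and a zero has no logarithm. That period then contributes essentially nothing to the Test/Reference ratio. What is at stake is a bioequivalence conclusion reached with the most adverse observation left out by rule. The study is open-label, so a decision on how to treat such a profile, if left until one appears, would be made with the treatment known.

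**Working it through.** **Inputs.** From SAP 9: 26 evaluable subjects, true ratio 1.05, within-subject CV 21%, limits 0.80 to 1.25, at least 90% power. From SAP 11.4.4: 90% CI, that is, two one-sided 5% tests. Assumed: the exposure f at which a failed profile would be kept, as a fraction of that subject's expected Test value. No LLOQ is given, so f runs from 20% to 1%.

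**Step 1: the plan's own figure.** s = √ln(1 + 0.21²) = 0.2077. With 13 subjects per sequence, SE = s × √[½(1/13 + 1/13)] = 0.0576 on 24 df. Exact two one-sided test power at ratio 1.05 is 87.6% for N = 24 and 90.1% for N = 26. The planned 26 reproduces.

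**Step 2: one failed Test profile, dropped.** This leaves 13 and 12 complete pairs; the subject's Reference period is ignored because it adds almost nothing to the ratio. Power is 88.9% at ratio 1.05 and 95.8% at ratio 1.00. The expected ratio is unchanged.

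**Step 3: the same profile, kept at f.**
- The ratio becomes 1.05 × f^(1/26). For f = 10%: 1.05 × 0.1^(1/26) = 0.961.
- The expected variance of the Test − Reference log differences becomes 2s² + (ln f)²(1 − 1/13)/24. For f = 10%: 0.0863 + 5.302 × 0.923/24 = 0.290. Half of that, 0.145, is the within-subject variance, so the apparent CV is √(e^0.145 − 1) = 39.5%.
- The CI half-width on the log scale is about 1.711 × √0.290 × √(2/13)/2 = 0.181, giving roughly 0.80 to 1.15.

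Pass probabilities come from 40,000 simulated trials per setting, shifting one subject's log difference by ln f. They are per parameter.

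| One failed Test profile | Ratio | Apparent CV | Median 90% CI | Pass, true ratio 1.05 | Pass, true ratio 1.00 |
|---|---|---|---|---|---|
| Dropped (SAP rule) | 1.05 | 21% | 0.95–1.16 | 89% | 96% |
| Kept at 20% | 0.99 | 31.2% | 0.86–1.14 | 80% | 61% |
| Kept at 10% | 0.96 | 39.5% | 0.80–1.15 | 44% | 22% |
| Kept at 5% | 0.94 | 49.1% | 0.75–1.17 | 7% | 2% |
| Kept at 1% | 0.88 | 75.5% | 0.64–1.21 | 0% | 0% |

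The ratio, CV and CI columns are for true ratio 1.05.

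**Step 4: two failed Test profiles, true ratio 1.05.** Dropped: 88%. Kept at 20%, 10%, 5%, 1%: 29%, 0.4%, 0%, 0%.

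**Step 5: a failed Form A profile.** The limits are reciprocal, so at a true ratio of 1.00 the same pass probabilities apply to one failed Reference profile.

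**Step 6: how often.** The documents give no failure rate. If each Test dose failed independently with probability p, the chance of at least one failure in 26 is 1 − (1 − p)^26: 2.6% at p = 0.1% and 23% at p = 1%. Both values of p are illustrations only.

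**The case against.** The strongest reply is that the exclusion has a technical reason: BLQ is set to zero, the model is on the log scale, and any substitute value is arbitrary. It is also treatment-neutral, and the failure is not hidden. Listings are produced, and SAP 11.4.2.1 enters BLQ as zero in the concentration summaries. Nothing in the documents suggests that non-release is expected; they describe ready absorption and within-subject CVs of 16% to 20%. All of this stands. It explains why a zero cannot enter the model, but not why a profile should leave the bioequivalence decision without its cause being examined.

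The floors are also open to challenge. With a peak at about 4 hours and single-exponential decline, the 96-hour level is 2^(−92/20) = 4% to 2^(−92/30) = 12% of Cmax. If the assay can measure typical 96-hour samples, a profile at 20% of normal exposure would not be entirely BLQ and would stay in under the SAP as written. That makes the upper rows of the table less relevant to this rule. It does not make the contrast smaller, since lower floors give lower pass probabilities.

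A reader might infer more than the documents support:
- That any poorly releasing Test capsule is removed. With one or two quantifiable values only AUC is lost; Cmax is primary, must also meet 0.80 to 1.25, and still counts against the form concerned.
- That one failure always decides the result. Kept at 20%, the study still passes with probability 80% (ratio 1.05) or 61% (ratio 1.00).
- That dropping pulls the ratio towards 1. At the planned 1.05 it stays at 1.05, whereas keeping the profile at 20% or 10% gives 0.99 or 0.96, both nearer 1. There the loss of power comes mainly from the inflated variance.
- That the rule favours Form C by design. It applies equally to Form A.

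**Conclusion.** The point holds for entirely BLQ profiles and, for AUC only, for profiles with too few quantifiable values. The SAP removes them because of the outcome and without a cause, and nothing else in the plan lets a complete release failure bear on the bioequivalence decision. For one failed Test profile at the planning assumptions, the rule means an 89% chance of passing instead of about 80% to 0%, depending on the floor. The contrast rests on 26 subjects, CV 21%, a single failure and an assumed floor. It is a range under assumption, not an estimate of error in this trial. The event should be rare, so this is a contingency to settle in advance. It does not show that the planned analysis would be wrong in the expected case, in which every profile is quantifiable.

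It would go too far to make an LLOQ-imputed analysis a mandatory condition for claiming bioequivalence, because its result depends heavily on the floor chosen. A documented cause review with a supportive analysis is the proportionate remedy.

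**What to change.** Amend the SAP before any PK model is run, including the PK analysis that SAP 12 describes as interim:

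1. **SAP 11.4.1.1 and 11.4.3.** An entirely BLQ profile, or an AUC set to NC for too few quantifiable values, is left out only when non-administration or a sampling or assay error is documented. The cause is reviewed for every such profile and reported by treatment before the analysis.
2. **SAP 11.4.4.** If no such cause is documented, a pre-specified sensitivity analysis is reported beside the primary result. It keeps the profile at a stated LLOQ-based value, identically for Form A and Form C. The text should give the value used for Cmax and how AUC0-t is built from it. LLOQ held flat over 96 hours is a larger share of a normal AUC than LLOQ is of a normal Cmax, so the two parameters will not sit on the same row of the table.
3. **Interpretation.** If the sensitivity analysis misses 0.80 to 1.25, the bioequivalence conclusion is qualified accordingly.
4. **SAP 11.1.** Amend the no-imputation sentence to permit this analysis.

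Protocol 9.4 already leaves the handling of missing and spurious data to the SAP or the study report, so a SAP amendment should suffice. The cost is a few sentences and one contingent model run per parameter. The downside is real: an unexplained failed profile may weaken the bioequivalence claim, and the sensitivity result depends on the floor chosen. The floor should therefore be fixed and stated in advance.
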